6.7.1.2 Tertiary Analyses

All tertiary analyses will be presented using descriptive statistics and analyzed using a t-test to compare the mean score of the cochlear implant Arm A to that of the hearing aid control Arm B at various time points. As these tertiary analyses are exploratory in nature, there will be no adjustment for multiple comparisons, no formal hypotheses testing and no statement of statistical significance.

Investigating treatment effect on:

- Neuropsychological outcomes:
 - Cogstate¹:
 - ☒ Detection Test – speed of performance
 - ☒ Groton Maze Learning Test – number of errors
 - ☒ Identification Test – speed of performance
 - ☒ One Card Learning Test – accuracy of performance
 - ☒ One Back Test – speed of performance
 - A6 vs B6 (treatment effect)
 - A0 vs B0 (population)
 - A6 vs B12 (6 months post-CI)
 - A12 vs B18 (12 months post-CI)
 - A0 vs A6 vs A12 (longitudinal treatment effect)
 - B6 vs B12 vs B18 (longitudinal treatment effect)
 - HI-MoCA:
 - ☒ A6 vs B6 (treatment effect)
 - ☒ A0 vs B0 (population)
 - ☒ A6 vs B12 (6 months post-CI)

¹ A sensitivity analyses will be conducted with test data integrity failures excluded if the integrity failure rate is greater than 10%.

Statistical Analysis Plan		Page 13 of 16
Sponsor	Study	CIP Version
Cochlear	Hearing Loss in Older Adults	9.0

- ☒ A12 vs B18 (12 months post-CI)
- ☒ A0 vs A6 vs A12 (longitudinal treatment effect)
- ☒ B6 vs B12 vs B18 (longitudinal treatment effect)
- Psychosocial measures:
 - UCLA Loneliness Scale:
 - ☒ A0 vs B0 (population)
 - ☒ A6 vs B12 (6 months post-CI)
 - ☒ A12 vs B18 (12 months post-CI)
 - ☒ A0 vs A6 vs A12 (longitudinal treatment effect)
 - ☒ B6 vs B12 vs B18 (longitudinal treatment effect)
 - Geriatric Depression Scale (GDS):
 - ☒ A0 vs B0 (population)
 - ☒ A6 vs B12 (6 months post-CI)
 - ☒ A12 vs B18 (12 months post-CI)
 - ☒ A0 vs A6 vs A12 (longitudinal treatment effect)
 - ☒ B6 vs B12 vs B18 (longitudinal treatment effect)
- Audiometric measures:
 - HHIE-S:
 - ☒ A0 vs B0 (population)
 - ☒ A6 vs B12 (6 months post-CI)
 - ☒ A12 vs B18 (12 months post-CI)
 - ☒ A0 vs A6 vs A12 (longitudinal treatment effect)
 - ☒ B6 vs B12 vs B18 (longitudinal treatment effect)
 - SSQ12:
 - ☒ A0 vs B0 (population)
 - ☒ A6 vs B12 (6 months post-CI)
 - ☒ A12 vs B18 (12 months post-CI)
 - ☒ A0 vs A6 vs A12 (longitudinal treatment effect)
 - ☒ B6 vs B12 vs B18 (longitudinal treatment effect)

Statistical Analysis Plan		Page 14 of 16
Sponsor Cochlear	Study Hearing Loss in Older Adults	CIP Version 9.0

[figure not shown]
- CNC words:
 - ☒ A0 vs B0 (population)
 - ☒ A6 vs B12 (6 months post-CI)
 - ☒ A12 vs B18 (12 months post-CI)
 - ☒ A0 vs A6 vs A12 (longitudinal treatment effect)
 - ☒ B6 vs B12 vs B18 (longitudinal treatment effect)
- AzBio Sentences:
 - ☒ A0 vs B0 (population)
 - ☒ A6 vs B12 (6 months post-CI)
 - ☒ A12 vs B18 (12 months post-CI)
 - ☒ A0 vs A6 vs A12 (longitudinal treatment effect)
 - ☒ B6 vs B12 vs B18 (longitudinal treatment effect)
- Audiometric thresholds
 - ☒ A0 vs B0 (population)
 - ☒ A0 vs A6 vs A12 (hearing preservation)
 - ☒ B6 vs B12 vs B18 (hearing preservation)
- Quality of life:
 - Health Utilities Index Mark III (HUI-III):
 - ☒ A0 vs B0 (population)
 - ☒ A6 vs B12 (6 months post-CI)
 - ☒ A12 vs B18 (12 months post-CI)
 - ☒ A0 vs A6 vs A12 (longitudinal treatment effect)
 - ☒ B6 vs B12 vs B18 (longitudinal treatment effect)

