Ancillary analyses	
Ancillary analyses include:
 
 Investigating treatment effect on neuropsychological measures using the Hearing Impaired Montreal Cognitive Assessment (HI-MoCA) at Follow-Up Visit 1 (FUV1). Investigate the treatment effect of immediate cochlear implantation vs continued use of HAs on psychosocial measures such as loneliness and depression using the UCLA Loneliness Scale and the Geriatric Depression Scale (GDS) at Follow-up Visit 1 (FUV1). Investigate the treatment effect of immediate cochlear implantation vs continued use of HAs on physical functioning measures such as daily activity and lifestyle using the Lifestyle Activity Questionnaire (LAQ) at Follow-up Visit 1 (FUV1). To determine the effect of treating hearing loss with CI versus continued use of HAs on quality of life in each arm (immediate CI vs continued HA use) using the Health Utilities Index Mark III (HUI-III) at Follow-up Visit 1 (FUV1). To quantify pre- to post-implantation outcomes associated with cochlear implantation. 
 Self-reported hearing ability using the Hearing Handicap Inventory for the Elderly – Screening (HHIE-S). Outcomes for both the treated ear and everyday listening condition (bimodal): speech perception in quiet using CNC Words presented 60 dBA and speech perception in speech-weighted noise using AzBio sentences presented at 65 dBA using a +10 dB Signal to Noise Ratio (SNR). Investigate maintenance of treatment effect on neuropsychological, psychosocial, physical, quality of life and audiometric measures obtained at: 
 FUV2 compared to FUV1 (Arm A). FUV3 compared to FUV2 (Arm B).

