6.1 Hearing interventions to reduce cognitive decline

Whether existing interventions for hearing loss can mitigate declines in cognitive function is unknown. Previous studies provide proof-of-principle that interventions that provide enhanced auditory stimuli can engage and modify the hypothesized mechanistic pathways linking hearing and cognition through reducing cognitive load (11-14), altering functional pathways and brain structure (4-10), and improving social engagement. A planned trial, the Aging, Cognition, and Hearing Evaluation Trial (ACHIEVE), will investigate the impact of best practice hearing health care, including the provision of hearing aids, on cognitive functioning in older adults with *mild-to-moderate* hearing loss.

The trial described in this protocol will be the first randomized controlled trial to investigate the impact of cochlear implantation versus continued use of hearing aids on cognitive function in individuals with severe-to-profound hearing loss. To date, only one published study has examined the effects of cochlear implantation on cognition in older adults (15). This longitudinal, multi-center study examined 94 adults aged 65-85 years who met candidacy requirements for a cochlear implant.

Neuropsychological tests, speech perception tests and quality of life and depression questionnaires were administered before cochlear implantation (baseline) and at 6 and 12 months post cochlear implant activation.

To avoid potential confounding effects of audibility and diminished speech perception understanding, all instructions for the neuropsychological tests were provided in written form in the Mosnier et al. study. The number of individuals with scores classified as abnormal decreased after implantation: At baseline, 25% of subjects had normal scores on six cognitive tasks, 31% had one abnormal score, 24% had two abnormal scores, and 20% had three abnormal scores. At 12 months, 40% had normal scores on six cognitive tasks, 33% had one abnormal score, 22% had two abnormal scores and only 5% had three abnormal scores. While informative, the Mosnier et al. study did not have a control arm, so it is possible that some of the improvement could be attributed to learning effects. The CI-Cognition trial described in this protocol incorporates a watchful waiting control arm and overcomes this limitation.

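### SAP 6.7.1.2 defines no within-arm estimate for the maintenance objective and labels uncontrolled change a treatment effect; HHIE-S is the outcome most exposed

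*SAP*

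**What the plan says.** **Objectives (Protocol, Synopsis, ancillary analyses).** One aim is "To quantify pre- to post-implantation outcomes associated with cochlear implantation", and it names HHIE-S, CNC words and AzBio sentences. Another is maintenance of effect, defined by two contrasts: "FUV2 compared to FUV1 (Arm A" and "FUV3 compared to FUV2 (Arm B". In the SAP's visit codes these are A12 vs A6 and B18 vs B12.

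**Planned rows (SAP 6.7.1.2).** The within-arm rows are "A0 vs A6 vs A12 (longitudinal treatment effect" for Arm A and "B6 vs B12 vs B18 (longitudinal treatment effect" for Arm B. Baseline in Arm B enters this section only through "A0 vs B0 (population", a between-arm check.

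**Planned method (SAP 6.7.1.2).** Tertiary outcomes are summarised descriptively and "analyzed using a t-test to compare the mean score of the cochlear implant Arm A to that of the hearing aid control Arm B". No paired, repeated-measures or other within-arm method is given. The section describes itself as exploratory and rules out statements of significance.

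**Rationale (Protocol 6.1).** An earlier cohort study of cochlear implantation and cognition is faulted because it "did not have a control arm, so it is possible that some of the improvement could be attributed to learning effects". The protocol says its own control arm removes that limitation.

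**The concern.** There are two gaps.

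First, a named protocol objective has no defined estimate. Maintenance is a question about the last two visits in each arm. The SAP never isolates those visits, and the one test it names needs two arms. Whoever runs the analysis would have to invent the method after seeing the data.

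Second, change from before to after implantation in a single arm mixes the implant with time, repeat testing, the review and counselling visits, and regression to the mean. Calling it a treatment effect claims more than it can show. Arm B passes through an observed six-month hearing-aid period before surgery (B0 to B6), so the comparator has been collected, but no change over that period is planned.

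HHIE-S has most at stake. Its baseline is the screening score, and that same score must reach 24 for entry. Subjects selected on a high score tend to score lower when measured again, and lower means less handicap. The A0 to A6 fall therefore probably includes some selection effect, and no randomized HHIE-S comparison is planned to remove it.

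**Working it through.** **1. The plan's own figure.** The SAP gives no figure for the within-arm rows. Its only related figure is the primary sample size of 12 per arm (SAP 5.1.1). With d = 3.0/1.8 = 1.667 and two-sided alpha 0.025, a two-sample t-test needs 9 per arm (power 84.4%). Then 9/(1 - 0.20) = 11.25, rounded up to 12. The figure reproduces, and nothing below touches it.

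**2. Objectives against planned rows.**

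| Question | Contrast needed | In the SAP |
|---|---|---|
| Maintenance, Arm A | A12 - A6 | Only inside A0/A6/A12 |
| Maintenance, Arm B | B18 - B12 | Only inside B6/B12/B18 |
| Concurrent change without implant | B6 - B0 | No row |
| Randomized comparison, SSQ12 | A6 vs B6 | 6.6.1, baseline-adjusted |
| Same, Cogstate | A6 vs B6 | 6.6.2 and 6.7.1.2 |
| Same, HI-MoCA | A6 vs B6 | 6.7.1.2 |
| Same, UCLA, GDS, CNC, AzBio, HUI-III | A6 vs B6 | 6.7.1.1 |
| Same, HHIE-S | A6 vs B6 | No row |

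**3. Is B6 the right starting visit for Arm B?** Yes. Protocol 9.3.10 places Arm B surgery about one week after FUV1, so B6 is the last visit before the implant. What is missing is the B0 to B6 comparator.

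**4. Where regression to the mean would fall for HHIE-S.** SAP 6.1.2 takes A0 and B0 for HHIE-S from screening (POV1), and the entry threshold applies at that visit. Selection therefore acts on A0 and B0, not on B6. The A0 to A6 change carries it and the B6 to B12 change should not. Because both randomized arms were selected in the same way, it cancels in expectation in (A6 - A0) - (B6 - B0) or in a baseline-adjusted A6 vs B6 comparison. The documents give no HHIE-S variance or reliability, so its size cannot be computed.

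**5. Precision of the missing estimates, SSQ12.** Inputs: at least 28 per arm (SAP 4) and change SD 1.8 (SAP 5.1.1). That SD describes change from before surgery to six months after activation. Using it for later intervals and for Arm B is an assumption, so a range is shown. With 20% attrition, 28 × 0.8 = 22.4, or 22 completers.

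- Paired change, 95% half-width = t(0.975, n-1) × SD/√n. At n = 28: 2.052 × 1.8/√28 = 0.70 points. For SD 1.2 and 2.4: 0.47 and 0.93. At n = 22 with SD 1.8: 0.80.
- Difference between concurrent changes, 95% half-width = t(0.975, 2n-2) × SD × √(2/n). At n = 28: 2.005 × 1.8 × √(2/28) = 0.96 points. For SD 1.2 and 2.4: 0.64 and 1.29. At n = 22 with SD 1.8: 1.10.

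Against the gain of 3.0 that the SAP assumes, a half-width of 0.70 is informative. Loss of half the gain is 1.5 points, or 1.5/0.70 = 2.1 half-widths. In 5,000 simulated trials (n = 28, SD of change 1.8 between any two visits), the paired 95% interval excluded zero in about 5% when the gain was kept, 99% when half was lost and 100% when all was lost.

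**The case against.** The strongest reply is that this is a gap in exploratory analyses and that the control arm is used where it counts. Much of that stands, and it rules out several stronger conclusions a reader might draw.

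- **That the whole pre-to-post objective is uncontrolled.** It is not. CNC and AzBio have A6 vs B6 rows in 6.7.1.1. The pairwise correlations named there do not compare means, but that is a separate fault. Among the three measures the objective names, only HHIE-S lacks the comparison. The objective also asks only to quantify outcomes; the treatment-effect label is the SAP's.
- **That the trial repeats the weakness it criticises in the earlier cohort.** That criticism concerns cognition. Cogstate and HI-MoCA both have A6 vs B6 comparisons, and Protocol 7 has the battery given twice before the intervention to limit learning. Any figure for residual practice would be an assumption.
- **That baseline in Arm B is never used.** SSQ12 baseline is a covariate in the primary model (SAP 6.6.1.1) and in the imputation (SAP 6.4). The narrower statement is true: no B0 to B6 change is planned.
- **That a lost gain could not be told from a kept one.** Visit means will be tabulated, so a fall would be visible. An omnibus three-visit test would fail here: under the assumptions in step 5 it is significant in about 100% of simulations whether the gain is kept, half lost or fully lost. But the SAP names no such test, and its rows could equally be read as pairwise comparisons.

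What the reply does not remove is that neither maintenance contrast has a stated estimate, interval or applicable method, and that HHIE-S gets only uncontrolled change under a causal label.

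**Conclusion.** The point holds in a limited form. SAP 6.7.1.2 provides no usable within-arm analysis for the maintenance objective, labels uncontrolled change a treatment effect, and omits the B0 to B6 change. The practical consequence is greatest for HHIE-S. This rests on the text of the two documents and needs no assumed inputs. The precision figures do depend on carrying the SAP's change SD of 1.8 to other intervals and to Arm B. The regression-to-the-mean concern follows from the entry rule, but its size is unknown. The analyses concerned are exploratory, and the primary result and the sample size do not change. The change should still be made: the gap is more than missing detail, and the data needed to close it are already scheduled.

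**What to change.** In SAP 6.7.1.2, for measures collected at the visits concerned:

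1. Report the paired mean changes A12-A6 and B18-B12 with 95% CIs as the maintenance result, and state the method (paired t, or one mixed model with these contrasts).
2. Report A6-A0 beside the concurrent B6-B0 change, with the between-arm difference and its 95% CI. Add a baseline-adjusted A6 vs B6 comparison for HHIE-S.
3. Relabel the within-arm treatment-effect rows *change after implantation*. The threshold rows already carry a hearing-preservation label and can stay.

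Do not use (B12-B6) minus (B6-B0) as the control. It assumes the same time or practice trend in both periods. For HHIE-S it would also subtract regression to the mean that falls only in the first period.

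Two related items can be settled in the same edit. LAQ is in the SAP visit table but in no analysis row, so the physical part of the maintenance objective has no analysis. HI-MoCA is marked only at POV1 and FUV1 in the protocol's procedures table, while Protocol 9.3.13 and 9.3.14 and the SAP expect it later; these passages need reconciling.

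The cost is SAP wording and a few more table lines, with no new visits or data. The downside is that gains attributed to the implant may look smaller.

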6.8 Safety Analyses

Adverse Events (AE) will be reported for the safety population by treatment arm and overall. AEs will be tabulated with the number of events and subjects with event for each event type and overall. Rates will be reported as the number of subjects who experience at least one event during the reporting interval out of the total number of subjects at risk at the beginning of the reporting interval. Serious adverse events will also be tabulated.

Adverse events leading to death or study discontinuation will be provided in listing format.

All device deficiencies will be reported in listing format.

Statistical Analysis Plan		Page 15 of 16
Sponsor Cochlear	Study Hearing Loss in Older Adults	CIP Version 9.0

6.9 Subgroup Analyses

No subgroup analyses are planned for the clinical investigation.

6.10 Interim Analyses

[figure not shown]
No interim analyses will be performed for the clinical investigation.

6.11 Protocol Deviations

Deviations from the procedures outlined in the CIP will be reported by investigational sites on the CRF. Protocol deviations will be summarized for all deviations and by type with event counts and number of subjects with at least one deviation.

7 Changes to Planned Analyses

Any changes to planned statistical analyses determined necessary prior to performing the analyses will be documented in an amended Statistical Analysis Plan and approved prior to the analysis when possible. Any other deviations or changes from the planned analyses deemed necessary due to violation of critical underlying statistical assumptions, data characteristics, or missing data will be clearly described in the clinical study report with justification and rationale.

Statistical Analysis Plan		Page 16 of 16
Sponsor Cochlear	Study Hearing Loss in Older Adults	CIP Version 9.0

Summary of Changes

Version	Effective Date	Summary of Changes	Change Author
1.0	MAY 6, 2019	Initial Release	[REDACTED]

8 Reference List

1. Claes AJ, Van de Heyning P, Gilles A, Van Rompaey V, Mertens G. Cognitive Performance of Severely Hearing-impaired Older Adults Before and After Cochlear Implantation: Preliminary Results of a Prospective, Longitudinal Cohort Study Using the RBANS-H. *Otol Neurotol*. 2018.
